5.1.1.2.5 Medical History

Medical and surgical history will be analyzed on the mITT population.

Medical history, encompassing abnormalities and surgeries reported as occurring before the Screening Visit, will be coded using the Medical Dictionary for Regulatory Activities (MedDRA), version 19.1 or newer. Unique subjects who report medical history events will be summarized by the primary system organ class (SOC) and preferred term (PT) (per MedDRA definition) for each treatment group and overall using frequency distributions.

5.1.1.2.6 Prior and Concomitant Medications

Prior and concomitant medications will be analyzed on the mITT population.

Prior medications include all medications with a start date before the day 1 date, whether or not medication is continuing beyond the baseline visit.

Concomitant medications encompass all non-study medications that the subject was taking prior to day 1 visit that are ongoing at the visit, in addition to all medications that have a start date on or after baseline (day 1) visit date.

Medications will be coded using the World Health Organization (WHO) Drug Dictionary, version March 2016 or newer. Unique subjects who reported medications will be summarized by Anatomical Therapeutic Chemical (ATC) 4 class and PT in total and by treatment group in mITT population. No statistical comparisons will be performed.

5.1.1.3 Efficacy Analyses

Efficacy analyses will be based on the mITT Population. Hypothesis testing will be 2-tailed with a significance level of 0.05, unless specified otherwise. Treatment comparison will be made for Setipiprant versus Placebo. For all efficacy analyses, no adjustment of significance levels will be made for multiplicity of treatment comparisons.

5.1.1.3.1 Collection and Derivation of Primary and Other Efficacy Measurements

The coprimary efficacy variables will be based on the following 2 measures: TAHC within a 1 cm² circular area on the left side of the scalp and SSA.

• The TAHC is a standardized objective quantification of each subject's number of terminal hairs (hair width $\geq 30 \ \mu m$) within a 1 cm² target circular area on the left side located at the anterior leading edge of the vertex thinning area of the scalp using digital image analysis.

[figure not shown]
• The SSA score is the subject's assessment of change of hair growth, scored on a 7-point scale (-3 = greatly decreased, -2 = moderately decreased, -1 = slightly decreased, 0 = remained the same, +1 = slightly increased, +2 = moderately increased, and +3 = greatly increased). The analyses of the SSA from the blinded photograph assessments will be based on the actual change from the screening photographs (ie, if the postbaseline photograph is used as Photo A, the assessment score will be reversed for analyses).

[figure not shown]
The coprimary efficacy endpoints based on the measurements of TAHC and SSA (blinded) are the following.

[figure not shown]
- Change from baseline in TAHC within a 1 cm² target circular area on the left side located at the anterior leading edge of the vertex thinning area of the scalp at Week 24
- Subject Self-Assessment of change from baseline in hair growth as viewed on the subject's paired (before and after presented in a blinded fashion) global photographs of the vertex target area at Week 24 and measured by the distribution of SSA scores

[figure not shown]
Postbaseline evaluations of TAHC and SSA will be made at Week 24 and 32, with the primary analysis timepoint being Week 24. For SSA, if the postbaseline photograph is used as Photo A, then the assessment score will be reversed for analyses.

For each of the 2 coprimary measures (TAHC and SSA), missing data will be imputed up to Week 24 using last observation carried forward (LOCF) method.

5.1.1.3.2 Primary Efficacy Analyses

[figure not shown]
For analyses of TAHC, the following set of hypotheses will be used to compare setipiprant tablets 1000 mg BID versus placebo BID:

[figure not shown]
- Null hypothesis: There is no difference between setipiprant tablets 1000 mg BID and placebo BID in increasing TAHC (terminal hairs in a 1 cm²circular area) as measured by the change from baseline at Week 24 using digital image analysis.
- Alternative hypothesis: There is a difference between setipiprant tablets 1000 mg BID and placebo BID in increasing TAHC (terminal hairs in a 1 cm² circular area) as measured by the change from baseline at Week 24 using digital image analysis.

For analyses of the SSA, the following set of hypotheses will be used to compare setipiprant tablets 1000 mg BID versus placebo BID:

- Null hypothesis: There is no difference between setipiprant tablets 1000 mg BID and placebo BID in SSA (blinded) of hair growth from baseline at Week 24.
- Alternative hypothesis: There is a difference between setipiprant tablets 1000 mg BID and placebo BID in SSA (blinded) of hair growth from baseline at Week 24.

Change from baseline in TAHC at Week 24 and SSA of the change of hair growth from baseline at Week 24 will be analyzed using an analysis of covariance (ANCOVA) model with treatment as a fixed effect and age and baseline value as covariates (if applicable). The treatment difference for setipiprant tablets 1000 mg BID versus placebo BID will be constructed based on this ANCOVA model, along with the 2-sided p-value.

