Two analysis populations are defined: modified intent-to-treat (mITT) and safety. The mITT population, consisting of all randomized subjects who have a baseline and at least 1 postbaseline primary efficacy measurement, will be used for analyses of efficacy data based on the randomized treatment group. The safety population, consisting of all treated subjects, will be used for analyses of all safety data based on the actual treatment received. Hypothesis testing will be 2-tailed with a significance level of 0.05. Pairwise comparisons of setipiprant tablets 1000 mg BID versus placebo will be made. The finasteride subjects enrolled prior to protocol Amendment 1 will be summarized alone and will not be included in the analysis models to compare with the other treatment groups. For all efficacy analyses, no adjustment of significance levels will be made for multiplicity of treatment comparisons.

Efficacy Analyses: The 2 coprimary efficacy variables are: 1) change from baseline in TAHC of terminal hairs/cm² within a 1 cm² circular area on the left side at Week 24; and 2) SSA of change from baseline in hair growth at Week 24. The 2 coprimary efficacy variables will be analyzed using an analysis of covariance (ANCOVA) model with treatment (excluding the finasteride group as described above) as a fixed effect and age and baseline value as covariates (if applicable). The treatment difference for setipiprant tablets 1000 mg BID versus placebo BID will be constructed based on this ANCOVA model, along with the 2-sided p-value.

Safety Analyses: All safety analyses will be performed on the safety population. Adverse events will be coded from the verbatim text into preferred term (PT) and primary system organ class (SOC) by using the Medical Dictionary for Regulatory Activities. The number and percent of subjects reporting treatment-emergent AEs at least once regardless of causality will be tabulated. Similarly, treatment-related AEs will be tabulated. The tables will be generated by primary PT and SOC as well as by severity. Safety data will be summarized by frequency distributions or descriptive statistics and described in the detailed analysis plan.

Sample Size Calculation: The study plans to enroll approximately 152 subjects in the setipiprant 1000 mg BID (n = 80) and placebo BID (n = 72) groups. Of the 152 subjects to be enrolled, 12 subjects will be randomized to the The remaining 140 subjects will be randomized

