5.4 Treatment Allocation Ratio and Stratification

. The 140 subjects will be randomized to setipiprant and placebo at a 1:1 ratio to be stratified by baseline age group (18 to 34 and 35 to 49 years).

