6.1.1.2 Subject Self-Assessment

The SSA (A12.1.7) is a coprimary measure that consists of a single item that assesses each subject's perception of change in scalp hair growth. The subject uses a standardized global photograph of his scalp taken at the screening visit (the screening photograph is defined as the subject's baseline) presented side by side with a standardized global photograph taken at the postbaseline visit to give a comparative score. The photographs are presented in a blinded and randomized manner, and response options are on a 7-point ordinal scale. Refer to the imaging vendor manual for the methodology for obtaining global photographs.

[figure not shown]

[figure not shown]

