7.5 Sample Size Calculation

7.6 Interim Analyses

No interim analyses are planned.

8. Study Visit Schedule and Procedures

Please see Figure 1 for a flow diagram of study design. Table 1 provides the schedule of visits and procedures.

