4.1 Primary Study Objectives and Design

The objectives of this study are to evaluate the safety, tolerability, and efficacy of oral administration of setipiprant tablets 1000 mg BID in males with androgenetic alopecia (AGA), Male

subjects aged 18 to 49 years (inclusive) at baseline, who are in general good health, have androgenetic alopecia with vertex patterns IIIv, IV, or V on the NHS, and are dissatisfied with

[figure not shown]
will be screened for eligibility for enrollment into the study.

All investigators, site staff, and subjects will be blinded to whether subjects receive setipiprant or matching placebo during the study.

Approximately 152 subjects will be enrolled in up to 20 US sites. On Day 1, 140 eligible subjects will be randomly assigned to 1 of 2 treatment groups in a 1:1 ratio to receive setipiprant tablets 1000 mg BID (hereafter referred as Setipiprant), or placebo BID (hereafter referred as Placebo), and

will be stratified by baseline age group

(< 35 and \ge 35 years). Overall, the number of subjects enrolled into the setipiprant and placebo groups will be about 80 and 72, respectively (Figure 4-1).

This SAP is based on the Amendment 1 of the protocol. The original protocol had three treatment arms – Setipiprant 1000 mg BID, Placebo BID and Finasteride 1 mg QD. The Finasteride 1 mg QD was removed from Amendment 1 of the protocol. Data in the Finasteride group will be summarized but not compared with the other treatment groups.

5. Statistical Methodology and Study Endpoints

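### Optional efficiency gain, not an error: the blinded SSA coprimary model has no term for photo presentation order, so any display-position effect stays in the residual

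*SAP*

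**What the plan says.** Protocol 6.1.1.2 describes the SSA as a single 7-point item on which the subject compares a screening photograph with a later one. On display it says: "The photographs are presented in a blinded and randomized manner". Because the rating follows the display, its sign has to be realigned. SAP 5.1.1.3.1, like Protocol 7.2, states that "if the postbaseline photograph is used as Photo A, the assessment score will be reversed for analyses".

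The blinded SSA at Week 24 is one of the two coprimary variables. SAP 5.1.1.3.2 and Protocol 7.3.1 give both coprimaries the same model: "analysis of covariance (ANCOVA) model with treatment as a fixed effect and age and baseline value as covariates (if applicable". The SSA is itself a rating of change and has no baseline value to enter, so its model reduces to treatment and age.

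The SAP's general method for ordinal data (5.1.1.1.3, a Cochran-Mantel-Haenszel row mean scores test) is stratified by age group only. The visible text has no presentation-order covariate, order stratum, balance rule or order-based sensitivity analysis.

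**The concern.** In a side-by-side comparison, a rater may lean towards one display position whatever the pictures show. Randomising the display stops such a lean from favouring either the earlier or the later photograph on average. Reversing the sign corrects the direction of the score. Neither step removes the lean from the individual score: after reversal it appears as +d in subjects shown one order and -d in those shown the other.

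Presentation order is a factor that the trial itself randomises, and the reversal cannot be done without knowing it. Leaving it out of the model puts any position effect into the residual variance of a coprimary endpoint in a trial of about 152 subjects. What is at stake is some precision and power, and nothing else.

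**Working it through.** **The plan's own figure.** SAP 4.1 says: "Overall, the number of subjects enrolled into the setipiprant and placebo groups will be about 80 and 72, respectively". The Protocol Summary says: "The study plans to enroll approximately 152 subjects in the setipiprant 1000 mg BID (n = 80) and placebo BID (n = 72) groups". Protocol 5.4 adds: "The 140 subjects will be randomized to setipiprant and placebo at a 1:1 ratio to be stratified by baseline age group". These agree as sums: 80 + 72 = 152 and 140 + 12 = 152. The power basis cannot be reproduced, because in the public text only the heading of Protocol 7.5 is visible.

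**Inputs.** From the documents: n = 80 and 72, and the test level ("Hypothesis testing will be 2-tailed with a significance level of 0.05", SAP 5.1.1.3). Assumed, because the documents do not give them: residual SSA SD 1.0 (range 0.8 to 1.2), position effect d from 0.1 to 0.5 points, and order split 50:50.

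**Mechanism.** Let c be the subject's perceived change, and let o = +1 if the postbaseline photograph is Photo B and -1 if it is Photo A. The displayed rating is o·c + d. After reversal the analysed score is o·(o·c + d) = c + o·d. With 50:50 order, its variance is SD² + d².

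**Closed form, SD 1.0.** √(1/80 + 1/72) = 0.1624. The standard error (SE) is 0.1624 without a position effect and 0.1624·√(1 + d²) with one left unmodelled. The difference detectable with 80% power at d = 0 is (1.960 + 0.842) × 0.1624 = 0.455.

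| d | Variance inflation d²/SD² | SE, no order term | Power, no order term (80% if d = 0) |
|---|---|---|---|
| 0.1 | 1% | 0.1633 | 79.6% |
| 0.2 | 4% | 0.1657 | 78.4% |
| 0.3 | 9% | 0.1696 | 76.5% |
| 0.5 | 25% | 0.1816 | 70.7% |

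**Sensitivity to SD**, with the difference reset each time to give 80% power at d = 0. At d = 0.3 the inflation is 14.1% (SD 0.8) or 6.2% (SD 1.2), and power is 74.6% or 77.6%. At d = 0.5 it is 39.1% or 17.4%, and power is 66.1% or 73.4%.

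**Simulation on the rounded 7-point scale.** Settings: 20,000 trials per d, SD 1.0, true difference 0.4 points, least squares with and without the order term.

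| d | Variance without v with term | Reduction | Power without v with term |
|---|---|---|---|
| 0.2 | 0.0295 v 0.0287 | 3% | 0.63 v 0.65 |
| 0.3 | 0.0307 v 0.0286 | 7% | 0.62 v 0.65 |
| 0.5 | 0.0348 v 0.0286 | 18% | 0.57 v 0.65 |

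For d up to 0.1 the reduction is about 0%. A separate simulation gave 2%, 6% and 17%, with power gains of about 1, 2 and 9 points. This is why ranges are quoted.

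The simulated reductions are a little below the closed-form d²/(1 + d²) of 3.8%, 8.3% and 20%. Rounding adds about 1/12 to the variance, and estimating the extra term costs about 1/150. At d = 0.5, for example, 0.25/(1 + 0.083 + 0.25) = 18.8%, less about 0.7%, is about 18%.

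**Validity.** In 10,000 runs per setting without the order term, type I error was 4.8% to 5.3%. The mean estimate under no effect was within about 0.002 of zero. Under a true effect the mean estimates with and without the term agreed to about 0.001.

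**Noise and chance imbalance are one cost.** A chance imbalance in order between arms shifts the estimate with SD 0.1624·d, which is 0.049 at d = 0.3. Its square is 0.0024. The unmodelled SE² minus the d = 0 SE² is 0.1696² - 0.1624² = 0.0288 - 0.0264 = 0.0024. The shift is therefore already inside the ordinary SE.

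**The case against.** The strongest reply is that the plan is valid as written. Random order is itself the design's control for position effects. It makes order independent of treatment, and the ordinary SE covers the extra variance. No passage reports or suggests a position effect. At d of 0.3 or less the gain is at most about 3 power points at SD 1.0. All of this stands, and it makes the point an optional improvement.

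Three stronger readings are tempting, and the documents do not support them.

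- **Bias or loss of type I error control, as when period is left out of a crossover.** In a crossover, treatment is tied to period within each subject. Here treatment is compared between subjects and order is randomised separately, so neither problem arises.
- **Chance order imbalance as a second cost.** It is the same variance counted again, as the working shows.
- **Comparing mean reversed SSA between the two orders as a check that reversal was done correctly.** A true position effect also separates those means. In the simulated setting the pooled mean change is 0.2 + 0.4 × 80/152 = 0.41. With d = 0.5, correctly reversed data give +0.91 and -0.09, while unreversed data give +0.91 and +0.09. The correct data look worse.

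Some relevant text is not visible: the SSA attachment, the imaging vendor's manual and SAP 5.1.1.3.3. Balancing of order within arm therefore cannot be excluded. It would remove the chance shift, but the d² would still sit in the residual variance unless order is modelled. It is also not visible whether order reaches the analysis dataset, or whether scores arrive already reversed.

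**Conclusion.** The coprimary SSA model omits a factor that the trial randomises and that the reversal step needs. This is a missed efficiency, and the planned analysis is valid without the term. The gain depends wholly on a position effect that the documents neither show nor size. With SD 1.0, 80 v 72 subjects and 50:50 order, it is nil for d up to 0.1, small at 0.2 to 0.3, and material only near 0.5, which is half the assumed SD. A smaller SD would make it larger, and a larger SD would make it smaller. Adding the term is worth considering because it costs almost nothing, but the plan does not depend on it.

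**What to change.** In SAP 5.1.1.3.2, before unblinding, add presentation order as a fixed effect in the Week 24 ANCOVA for the blinded SSA only. Code it +1 if the postbaseline photograph was Photo B and -1 if it was Photo A. SAP 6.5 carries earlier or baseline values forward, so a rule is needed for those scores: use the order at the visit that supplied the score, and 0 where no pair was rated. Confirm that the order variable is delivered to the analysis dataset.

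Verify the sign reversal record by record against the recorded photo assignment, and do not rely on comparing means by order.

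The cost is 1 degree of freedom out of about 150 and the carry-forward coding rule. If the position effect is small, little or nothing is gained. The term should be fixed before unblinding, because adding it later would look data-driven.

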4.1 Number of Subjects

Approximately 152 subjects will be randomized to 1 of 2 treatment groups (setipiprant 1000 mg BID, n = 80; placebo BID, n = 72) at up to 20 study centers in the US.

Approximately 140 subjects will be randomized in a 1:1 ratio to group (setipiprant 1000 mg BID, placebo BID), and stratified by baseline age, 18 to 34 and 35 to 49 years.).

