5.1.1.1 Common Conventions

5.1.1.1.1 Analysis Populations

Two populations will be used in the analysis: modified intent-to-treat (mITT) and safety.

The mITT population, consisting of all randomized subjects who have a baseline and at least 1 postbaseline measurement for 1 of the coprimary efficacy measures, will be used for analyses of efficacy data based on the randomized treatment group. All efficacy variables will be summarized and analyzed using the mITT population. Demographic and baseline characteristics will also be based on mITT population.

The safety population, consisting of all subjects who receive at least 1 dose of study drug (ie, all treated subjects), will be used for analyses of all safety data based on the actual treatment received.

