5.1.1.1.3 Statistical Methodology

The methodologies defined below apply as specified to individual endpoints defined in this SAP. Finasteride subjects enrolled prior to Protocol Amendment 1 will be summarized alone and will not be included in the analysis models. All statistical testing will be based on 2-sided hypothesis tests with a statistical significance of $p \le 0.05$, unless specified otherwise.

- Descriptive statistics include the sample size (N), mean, standard deviation (SD), median, minimum (Min), and maximum (Max) for continuous/ordinal data, and the sample size (N), frequency count, and percentage for categorical data.
- For the analysis of ordinal-scaled categorical data, unless specified otherwise, Cochran-Mantel-Haenszel (CMH) row mean scores test stratified by age group (< 35 and ≥35 years) will be used.
- Change from baseline (CFB) will be analyzed using an analysis of covariance (ANCOVA) model with treatment as a fixed effect and age and baseline value as covariates (if applicable). The treatment difference (Setipiprant versus Placebo) will be constructed based on the ANCOVA model, along with the 2-sided p-value and 95% confidence intervals (CI). The type III sums of squares will be used for all ANCOVA models.

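### The 12 separately randomised subjects are pooled with the 140 in the coprimary ANCOVA without a term for randomisation cohort, although the two cohorts appear to have different allocation ratios

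*SAP*

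**What the plan says.** The Protocol Summary (Sample Size Calculation) separates a small group from the rest: "Of the 152 subjects to be enrolled, 12 subjects will be randomized to the", after which the text is redacted. Protocol 5.4 covers the others: "The 140 subjects will be randomized to setipiprant and placebo at a 1:1 ratio", stratified by age group. Protocol 4.1 gives the totals: "Approximately 152 subjects will be randomized to 1 of 2 treatment groups (setipiprant 1000 mg BID, n = 80; placebo BID, n = 72". SAP 4.1 has the same structure, with "140 eligible subjects will be randomly assigned to 1 of 2 treatment groups in a 1:1 ratio" and then "the number of subjects enrolled into the setipiprant and placebo groups will be about 80 and 72, respectively".

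The amendment log (Protocol 12.4, entry for Section 5.4) describes the age-stratified subjects as non-PK. The 12 therefore look like a pharmacokinetic group outside the age stratification.

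Efficacy is analysed in the mITT population, "consisting of all randomized subjects who have a baseline and at least 1 postbaseline measurement for 1 of the coprimary efficacy measures" (SAP 5.1.1.1.1). No visible text leaves out the 12. The primary model is given in SAP 5.1.1.3.2 as an ANCOVA "model with treatment as a fixed effect and age and baseline value as covariates (if applicable". SAP 5.1.1.1.3 and Protocol 7.3.1 have the same terms.

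**The concern.** Within each cohort the comparison is randomised. If the allocation ratios differ and the cohorts are pooled without a cohort term, the 12 make up a larger share of the setipiprant arm than of the placebo arm. Any outcome difference between cohorts that age and baseline do not explain then shifts the treatment estimate. For the Subject Self-Assessment (SSA), which is itself a change score, a baseline value may not apply, so age may be the only adjustment.

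The model already includes age, the one visible stratification factor. Cohort is the visible feature of the randomisation that it leaves out. At stake is whether the type I error and the estimate for each coprimary depend on an assumption the visible SAP neither states nor checks: that the cohorts have the same expected residual outcome.

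**Working it through.** **Planned numbers.** 80 + 72 = 152 and 152 − 140 = 12, as stated. The pre-amendment counts agree: 187 − 35 = 152, 187 − 175 = 12, and 175 at 2:2:1 is 70:70:35.

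**Implied split of the 12.** 140 at 1:1 is 70 per arm; 80 − 70 = 10 and 72 − 70 = 2. This is an inference. Because the totals are approximate, 9:3 (totals 79 and 73) and 8:4 (78 and 74) are also possible.

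**Share of a residual cohort difference entering the estimate.** With a and b cohort subjects in the setipiprant and placebo arms, the share is a/n(setipiprant) − b/n(placebo):

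- 10:2: 10/80 − 2/72 = 0.0972
- 9:3: 9/79 − 3/73 = 0.0728
- 8:4: 8/78 − 4/74 = 0.0485

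More extreme splits are equally unseen and would raise it: 12.2% at 11:1 and 14.6% at 12:0.

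**Effect on error rates.** Simulation used 1,000,000 trials per scenario: 70/70 plus the 12, outcome = 0.1 × age + 0.3 × baseline + d × cohort + N(0,1), no treatment effect, and a t test at two-sided 0.05. The residual cohort difference d is an assumption, with the 12 taken to do better. Entries are the planned model's error per endpoint, two-sided (nominal 5%) / in setipiprant's favour (nominal 2.5%), in percent. Monte Carlo standard error is at most 0.03 points.

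| Split | d = 0 | d = 0.25 SD | d = 0.5 SD | d = 1.0 SD |
|---|---|---|---|---|
| 10:2 | 4.98 / 2.51 | 5.18 / 3.45 | 5.79 / 4.64 | 8.04 / 7.59 |
| 9:3 | 5.01 / 2.49 | 5.07 / 3.17 | 5.37 / 3.96 | 6.34 / 5.66 |
| 8:4 | 5.00 / 2.49 | 5.00 / 2.91 | 5.06 / 3.36 | 5.15 / 4.14 |

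With a cohort term, all 12 scenarios give 4.98% to 5.05% two-sided and 2.48% to 2.52% in favour. Mean bias at d = 1.0 and 10:2 falls from 0.0974 SD to 0.000.

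**Precision of the adjusted model at 10:2 (SD units).**

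- Planned: √(1/80 + 1/72) = 0.1624
- With cohort term: √(1/[35 + 1/(1/10 + 1/2)]) = 0.1651, ratio 1.0166 (1.0092 at 9:3, 1.0041 at 8:4)
- The 140 alone: √(2/70) = 0.1690
- Weight of the 12 in the adjusted contrast: 1.667/(35 + 1.667) = 4.5%, leaving 95.5% to the 140

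**Power at an assumed effect of 0.45 SD** (noncentral t, 148, 147 and 136 degrees of freedom): 78.6% planned, 77.2% with the cohort term, 75.3% on the 140 alone.

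**The case against.** The strongest reply is that the decisive text is redacted and no harm is shown. The purpose, ratio, stratification and any separate analysis of the 12 are unseen. Protocol 7.5 is blank, and SAP 5.1.1.3.3 and 5.1.2 are referred to but not visible. Dosing, eligibility, blinding, image-based hair counts and blinded-order photographs are, as far as can be seen, common to everyone. PK status has no evident route to a Week 24 hair count. If entry to the 12 were itself random, the expected difference would be zero. All of this stands, and it is why the point is conditional. It does not change the primary model sentence, which is legible in full and has no cohort term.

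The sign of d is also assumed. In a treatment-only simulation (40,000 runs, 10:2) with the 12 doing worse by 0.5 SD, favourable error falls to about 1.2%. Averaged over the two signs it is (4.64 + 1.2)/2, about 2.9%. That is fair: the two-sided figures are the ones to judge by, since the planned test is two-sided. The simulation also resembles the hair count more than the 7-point SSA, though this probably matters little numerically.

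Finally, one could run only the sensitivity analysis and keep the full power of the planned model. That is defensible, but it would leave the primary p-values resting on an unstated assumption to save about 1.4 points of power.

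**Conclusion.** The point holds as a minor one. On the visible text, two randomisations that appear to use different ratios are pooled without a term for the randomisation a subject came from. The best single figure is 9.7% of any residual cohort difference, because 10:2 fits the stated totals exactly; 8:4 to 10:2 gives roughly 5% to 10%.

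Two-sided error inflation is material only near 10:2, less so at 9:3, and only for differences of 0.5 SD or more. At 8:4 it stays close to 5%. If success requires both coprimaries, the trial-level risk is lower; the decision rule is not visible.

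Confidence is medium. The conclusion rests on the inferred split, on assumed cohort differences, and on the redacted sections not already handling the 12. The reason to act is that the analysis should follow the randomisation and that doing so costs very little.

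**What to change.** In SAP 5.1.1.1.3 and 5.1.1.3.2, Protocol 7.3.1 and the Protocol Summary, specify both coprimary ANCOVAs with treatment and randomisation cohort (12-subject versus 140-subject) as fixed factors, keeping age and, where applicable, baseline value as covariates. Prespecify a sensitivity analysis on the 140 alone with the planned model. State that if no placebo subject among the 12 enters mITT, that cohort contributes nothing to the adjusted contrast. If redacted text already has a cohort term or this sensitivity analysis, align the primary model sentence with it. Record the change in SAP 5.2.2, which now reads as not applicable.

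The cost is text edits and one degree of freedom. With no cohort difference, the standard error rises 1.7% at 10:2, 0.9% at 9:3 and 0.4% at 8:4. At 10:2 it rises 2.3% if one of the two placebo subjects is missing from mITT (√(1/[35 + 1/(1/10 + 1)]) / √(1/80 + 1/71) = 1.0235) and 3.3% if both are (0.1690/√(1/80 + 1/70) = 1.0328). If the cohorts do differ by 1.0 SD, the adjusted standard error at 10:2 is 1.8% smaller than the planned one.
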